**Table 3 MEDI-573 does guideline (Cohorts 1 and 2)**

AE	Action	Guidance for dosing of MEDI-573
Grade $\leq$ 1	Continue	None
Grade 2	Continue	
 
1) Withhold MEDI-573 for other than above up to 7 days until the toxicity resolves or reverts to <math>\leq</math>Grade 1 or baseline and resume at current dose level.
 
2) Any infusion reaction that responds to medical therapy or slowing the infusion rate.
 

	Discontinue	
 
1) Discontinue MEDI-573 if MEDI-573 is withheld for <math>>7</math> days without resolution of toxicity to <math>\leq</math>Grade 1 or baseline.
 
2) Toxicity that causes a cumulative delay of <math>\geq 21</math> days in 3 consecutive cycles.
 
3) Any infusion reaction that does not respond to medical therapy or slowing the infusion rate.
 
4) Any allergic reaction or infusion reaction that necessitates the use of systemic pressor agents.
 

Grade 3 or 4	Continue	
First Occurrence:
 
Treatment at the current dose level may be resumed only after recovery of the toxicity is confirmed to be <math>\leq</math>Grade 1 or baseline level during 7 days (at the longest) of cessation of the drug, and clinical benefit has been documented. However, treatment should be discontinued if an AE corresponding to DLT occurs.

	Discontinue	
First Occurrence:
 
 
1) Discontinue MEDI-573 if no clinical benefit has been documented.
 
2) Discontinue MEDI-573 if MEDI-573 is withheld for <math>>7</math> days without resolution of toxicity to <math>\leq</math>Grade 1 or baseline, even if clinical benefit has been documented.
 
3) Grade 3 or greater allergic or infusion reactions.
 
 
Second Occurrence:
 
Discontinue MEDI-573.

Date

**Table 4**                      **MEDI-573 does guideline (Cohort 3)**

AE	Action	Guidance for dosing of MEDI-573
Grade $\leq$ 1	Continue	None
Grade 2	Continue	
 
1) If the toxicity resolve to <math>\leq</math>Grade 1 or baseline level by Day 1 of the subsequent cycle, treatment at the current dose level may be resumed.
 
2) Any infusion reaction that respond to medical therapy or slowing the infusion rate
 

	Discontinue	
 
1) Discontinue MEDI-573 if the toxicity does not resolve to <math>\leq</math>Grade 1 or baseline level by Day 1 of the subsequent cycle.
 
2) Toxicity that causes a cumulative delay of <math>\geq</math>21 days in 3 consecutive cycles
 
3) Any infusion reaction that does not respond to medical therapy or slowing the infusion rate.
 
4) Any allergic reaction or infusion reaction that necessitates the use of systemic pressor agents
 

Grade 3 or 4	Continue	
First Occurrence:
 
If the toxicity resolve to <math>\leq</math>Grade 1 or baseline level by Day 1 of the subsequent cycle and clinical benefit has been documented, treatment at the current dose level may be resumed. However, treatment should be discontinued if an AE corresponding to DLT occurs

	Discontinue	
First Occurrence:
 
 
1) Discontinue MEDI-573 if no clinical benefit has been documented.
 
2) Discontinue MEDI-573 if the toxicity does not resolve to <math>\leq</math>Grade 1 or baseline level by Day 1 of the subsequent cycle, even if clinical benefit has been documented.
 
3) Grade 3 or greater allergic or infusion reactions.
 
 
Second Occurrence:
 
Discontinue MEDI-573.

### 5.1.9 Duration of therapy

Subjects may continue to receive MEDI-573 as long as they are continuing to show clinical benefit, as judged by the investigator or sub-investigator, no safety concerns, and in the absence of discontinuation criteria (ie, confirmation of disease progression ) provided that separate written consent on continuous participation in the study is obtained from the subjects upon proceeding from Cycle 1 to Cycle 2.

Subjects may repeat this schedule, until no clinical benefit is apparent (ie, subject has progressive disease), or the subjects withdraw their consent.

Date

### **5.1.10 Treatment compliance and accountability**

Investigational product will not be distributed to the study site until the contract is concluded between the study site and AstraZeneca. The investigational product should only be used as directed in this protocol. The Investigational Product Storage Manager is responsible for managing the investigational product from receipt by the institution until the return of all unused investigational product to AstraZeneca. AstraZeneca will provide the study documents 'Procedures for drug accountability' and 'Procedures for drug storage' which describes the specific requirements.

Record on investigational product distribution and records on use, destruction and return should be available for verification at the time of study completion. Record on use should include subject identification information, amount and date of prescription, and amount of unused investigational products returned to the investigator(s). Explanation should be provided using the specified form for any inconsistency. The head of the study site or the Investigational Product Storage Manager will sign the certificates of delivery and collection. Empty vials will be disposed of by the medical site.

Details of treatment with investigational product for each subject will be recorded in the Case Record Form.

## **5.2 Rationale for dose regimen**

In a preclinical study, MEDI-573 was administered to cynomolgus monkeys repeatedly as an IV infusion at doses up to 60 mg/kg weekly for 13 weeks, and there was no evidence of toxicity. This result indicated that the no observable adverse effect level (NOAEL in cynomolgus monkeys is higher than 60 mg/kg, which is estimated to be equivalent to higher than 19 mg/kg in human on the basis of body surface area of monkey and human (conversion factor 3.1).

In the US study MI-CP184, up to Feb. 17, 2011, twenty-five subjects with advanced solid tumours were enrolled in 6 cohorts in dose-escalation phase and dose expansion phase of 15 mg/kg. There has been ever no DLTs. (See Section 2.2.2). These results demonstrated the safety and tolerability of MEDI-573 administered weekly at doses up to 15 mg/kg. Thus the safety and tolerability of the starting dose of the scheduled Japanese study (5.0 mg/kg) have been demonstrated in Study MI-CP184.

Consequently, since the above results showed the NOAEL in cynomolgus monkeys is estimated to be equivalent to higher than 19 mg/kg in human and the safety of MEDI-573 up to 15 mg/kg was demonstrated in Study MI-CP184. In addition, the regimen (Cohort 3) that is administration of every 21 days is one of the dose regimens is plan to examine in the development program in the future. As for this regimen, it is plan to execute it in the MI-CP184 study.

Whether to proceed and the dose for the next cohort will be determined based on the safety, tolerability and PK data (if available) of MEDI-573 collected in the cohort in reference to the results of Study MI-CP184.

Date

### 5.3 Benefit/risk and ethical assessment

MEDI-573 is a fully human mAb directed against IGF-I and IGF-II. IGF-I and IGF-II bind to receptors (IGF-IR and IR-A) as ligands activating the downstream signaling and thus are involved in regulating cell survival, proliferation, and differentiation. On the other hand, excessive activation of IGF signals has been reported in various tumours, and IGF-I and IGF-II are drawing attentions as signalling pathway deeply involved in tumour development, growth and progression through the powerful mitogenic and anti-apoptotic activity. MEDI-573 directly captures and neutralises the IGF-I and IGF-II ligands inhibiting the IGF signalling pathway. MEDI-573 has been shown to inhibit tumour growth in a wide range of human cancer models as a single agent and in combination with chemotherapy. Nonclinical studies suggest that MEDI-573 has the potential to achieve broad anti-tumour efficacy owing to its ability to inhibit both IGF-IR and IR-A pathways.

Antibody drugs against IGF-IR have no effect on IR-A, and so no effect on tumours which highly express IR-A leading to increased mitogenic signalling through IR-A. Also IGF-IR kinase inhibitors inhibit both IGF-IR and IR-A/IR-B, which have identical kinase domains. IR-B plays an important role in insulin signalling and glucose metabolism, and as a result, is strongly associated with glucose metabolism abnormal such as hyperglycaemia as adverse drugs reactions. Furthermore, MEDI-573 has potential to achieve this without perturbing glucose homeostasis, which has been an endocrine liability of other investigational agents that target IGF-IR ([Gao et al, 2011](#)).

In non-clinical safety studies, MEDI-573 was well tolerated with no evidence of test-article related toxicity. In the ongoing Phase 1 study (MI-CP184) of MEDI-573 in solid tumours, MEDI-573 has been well tolerated until 15 mg/kg. In this study, adverse events observed to date have been consistent with established conditions in the study population, with the most common AEs being decreased appetite, fatigue, and gastrointestinal events such as nausea and diarrhea. No DLTs have been observed to date. If toxicities reported in studies of other investigational agents that target the IGF axis are based on activity against IGF-IR, it is possible that the following AEs may be observed, such as hyperglycemia, anorexia, nausea, diarrhea, weight loss, elevated transaminases, anemia, thrombocytopenia, pruritus, rash, arthralgia, paresthesia, fatigue, autoantibody production and infusion reactions ([Weroha and Haluska, 2008](#)).

Based on published literature with similar therapies (ie, monoclonal antibodies targeting IGF signaling pathway), observed AEs were generally mild (Grade 1 or 2) and included hyperglycemia, gastrointestinal disturbances, hypersensitivity reactions, pruritus, asthenia, and anemia ([Haluska et al, 2007](#); [Atzori et al, 2008](#)). Other toxicities included Grade 3/4 thrombocytopenia ([Tolcher et al, 2008](#); [Hidalgo et al, 2008](#)), Grade 3 hyperglycemia ([Higano et al, 2007](#)), Grade 3 purpura ([Atzori et al, 2008](#)), Grade 4 uric acid increase, and Grade 3 bilateral deep venous thrombosis ([Olmos et al, 2008](#)).

Since MEDI-573 is an antibody drug, subjects may experience an infusion reaction during infusion of MEDI-573, so all subjects in this study will be closely monitored during the treatment period and throughout the study period.

Date

The potential risk for pain and local irritation at the infusion site is likely to be clinically predictable and be treatable symptomatically. Finally, collection of blood samples for PK sampling will be collected from a vein other than that used to infuse MEDI-573.

No reproductive toxicology nor teratogenic studies have been conducted with MEDI-573 to date, and it is unknown whether the drug is excreted in human milk. Therefore, women of childbearing potential and men should agree to use adequate contraception prior to study entry and for the duration of study participation and women who are breast feeding are excluded from the study. Both women and men should be fully informed of the lack of reproductive toxicity testing, and women must have a negative pregnancy test prior to enrolment for inclusion in this study.

As described, the study design aims to evaluate safety and tolerability while minimizing potential risks and although the potential benefits in patients are unknown at this time, non-clinical data demonstrate evidence of anti-tumour activity. Thus the benefit/risk assessment for this first time in patient phase 1 study appears acceptable for Japanese patients with advanced solid tumours for whom there is no alternative standard therapy.

## **5.4 Discontinuation of investigational product and withdrawal from study**

### **5.4.1 Interruption or Discontinuation of Study Dosing in Individual Subjects**

Subjects may be discontinued from investigational product in the following situations:

- Subject decision. The subject is at any time free to withdraw his/her participation in the study, without prejudice
- AEs requiring discontinuation of investigational product
- Severe non-compliance to this protocol as judged by the investigator and/or AstraZeneca
- Confirmed disease progression
- Subjects incorrectly initiated on investigational product (Section [5.4.3](#))
- Lost to follow up
- Pregnancy or intent to become pregnant
- DLT (see Section [5.1.4](#) for definition of DLTs)
- Treatment with another investigational agent
- Initiation of alternative anticancer therapy

Date

- Infusion reactions  $\geq$  Grade 2 that do not respond to medical therapy or slowing the infusion rate and are not of limited duration
- Grade 3 or greater allergic or infusion reactions. Any allergic or infusion reaction that necessitates the use of systemic pressor agents will cause dose discontinuation in that subject

In Cycle 2 or later, in addition to the above, refer to [Table 3](#) and [Table 4](#).

Subjects who are permanently discontinued from investigational product will discontinue the study (see Section [5.4.4](#)).

Subjects that are withdrawn from the study but are evaluable per the definition in Section [5.1.6](#) will not be replaced. Any subject that is withdrawn and is not evaluable will be replaced to ensure a minimum number of evaluable subjects.

Subjects may withdraw from any aspects of the voluntary exploratory research (see Section [6.7](#)) at any time, without prejudice to further treatment and independent of any decision concerning participation in other aspects of the main study. Procedures for withdrawal from the exploratory research are outlined in Section [6.8.5](#).

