#### **5.1.4 Definition of dose-limiting toxicity**

DLT will be graded according to the NCI CTCAE V4.0 and will be assessed from Cycle 1, Day 1 through Cycle 1, Day 21.

A DLT is defined as:

1. Any Grade 3 or higher non-haematologic toxicity that occurs during the DLT assessment period where a cause other than the investigational product cannot be reasonably justified with the following exceptions:
  - Grade <4 high glucose (fasting) with a duration of <24 hours after administration of MEDI-573
  - Grade 3 fever (in the absence of neutropenia) defined as >40.0°C (39.5°C in the axilla) that resolves to normal or baseline within 24 hours of treatment and is not considered an SAE
  - Grade 3 rigors/chills that respond to optimal therapy
  - Any isolated or transient laboratory changes without associated clinical signs or symptoms.
2. Any Grade 3 or higher haematologic toxicity that occurs during the DLT assessment period where a cause other than the investigational product cannot be reasonably justified.

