### 5.1.8 Guidelines for administration of MEDI-573 (after cycle 2)

It is not allowed to delay or modify during Cycle 1.

Dose interruption or discontinuation of MEDI-573, following the first cycle of treatment, will be determined based on AE (see Table 3 and Table 4). In addition, MEDI-573 be able to continue if events occurred is those clearly attributable to another cause such as disease progression or accident, not clinical significant lab abnormality, and not clinically significant and can be controlled by medication. . In Cycle 2 or greater, dosing interval should be 6 days or longer in Cohorts 1 and 2, and 20 days or longer in Cohort 3.

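### Section 5.4.1 makes stopping after a DLT permissive, and the firmer rule starts only in Cycle 2, so no sentence requires a weekly-cohort subject with a Cycle 1 DLT to stop before the Day 8 or Day 15 dose

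*Protocol*

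**What the plan says.** Section 3.1 sends the reader to Section 5.4.1 for the rules on stopping an individual subject. That section begins: "Subjects may be discontinued from investigational product in the following situations". The list that follows includes DLT and Grade 3 or greater allergic or infusion reactions. One sentence in the same list is mandatory: "Any allergic or infusion reaction that necessitates the use of systemic pressor agents will cause dose discontinuation in that subject".

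Section 5.4.1 then adds Tables 3 and 4 for later cycles only: "In Cycle 2 or later, in addition to the above, refer to" those tables. Section 5.1.8 sets the same limit: "Dose interruption or discontinuation of MEDI-573, following the first cycle of treatment, will be determined based on AE". Table 3 (Cohorts 1 and 2) says "However, treatment should be discontinued if an AE corresponding to DLT occurs" and puts "Grade 3 or greater allergic or infusion reactions" under its discontinue action. Table 4 does the same for Cohort 3.

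DLTs, by Section 5.1.4, "will be assessed from Cycle 1, Day 1 through Cycle 1, Day 21". For Cycle 1 dosing, Section 5.1.8 says: "It is not allowed to delay or modify during Cycle 1".

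**The concern.** The stopping rule for a DLT is worded more weakly in Cycle 1, the only cycle in which a DLT is defined, than in later cycles, where an event merely resembling one should end treatment. Section 5.4.1 shows that mandatory wording was available, because it is used for reactions needing pressor agents, yet DLT is left under the permissive lead-in.

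This matters in the weekly cohorts because further infusions fall inside the DLT window. Delay and modification are not available in Cycle 1, and under Section 3.1 a subject who does not receive every dose of a cycle leaves treatment. After a Cycle 1 DLT the investigator has two options: the next full dose on schedule, or stopping. The protocol does not say which. What is at stake is another full dose given to someone who has just had a limiting toxicity.

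**Working it through.** **Step 1. Is there an express Cycle 1 stop for a DLT?** The relevant sections are:

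| Section | Content | Requires stopping for a Cycle 1 DLT? |
|---|---|---|
| 5.4.1, list | DLT listed under a permissive lead-in | No |
| 5.4.1, pressor sentence | Mandatory, any cycle | Only if pressors are needed |
| 5.1.8, Tables 3 and 4 | Firmer wording | No, after Cycle 1 only |
| 3.1, dosing | Continues until toxicity is unacceptable | Implied; the term is not tied to DLT |
| 3.1, evaluability | Describes subjects who stop because of a DLT | Implied; it defines who counts |
| 5.1.6, evaluability | Having had a DLT in Cycle 1 is enough | No mention of stopping |
| 5.1.9 | Treatment needs absence of safety concerns and of discontinuation criteria | Implied |
| 5.4.2 | Study-wide halt for drug-related death, anaphylaxis, or events the study team physician judges serious enough | Only for those events |

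The answer is no. Stopping can be inferred, but it is not stated.

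**Step 2. Doses left after a Cycle 1 DLT.** Cohorts 1 and 2 are dosed on Days 1, 8 and 15 (Section 3.1), at 5.0 and 15 mg/kg (Table 2).

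- DLT before the Day 8 infusion: 2 doses left, 2 × 5 = 10 mg/kg or 2 × 15 = 30 mg/kg.
- DLT between the Day 8 and Day 15 infusions: 1 dose left, 5 or 15 mg/kg.
- DLT after the Day 15 infusion: none left.
- Cohort 3: one dose per cycle, none left.

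**Step 3. How many subjects could be in that position?** Take the Section 5.1.3 rules with all subjects evaluable, no intermediate dose, and the same assumed DLT rate p in each cohort. Write

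- a = (1 − p)³, the chance of no DLT in three subjects;
- c = 3p(1 − p)², the chance of exactly one in three;
- T = a + c·a, the chance that a dose is tolerated;
- e = 3p(1 + c), the expected DLTs in a cohort that is opened.

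Expected DLT subjects in Cohorts 1 and 2, including the top-up of the lower dose to six after a non-tolerated dose:

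E = e(1 + T) + 3p·a(1 − T)(1 + T)

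At p = 10%: a = 0.729, c = 0.243, T = 0.906, e = 0.373, so E = 0.711 + 0.039 = 0.75.

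For an upper rate, Section 2.2.2 gives 4 US subjects at 5.0 mg/kg and 10 at 15 mg/kg, both weekly, with no DLT. The one-sided 95% upper bound for 0 of 14 is 1 − 0.05^(1/14) = 19.3%. The 14 are enrolled subjects; the number evaluable for DLT is not stated.

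The timing of DLTs is also an assumption. Uniform timing puts 14/21 = two-thirds before the Day 15 infusion; one-third is shown as an alternative.

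| Assumed p | E | Dose still due, 2/3 before Day 15 | Dose still due, 1/3 before Day 15 |
|---|---|---|---|
| 5% | 0.34 | 0.23 | 0.11 |
| 10% | 0.75 | 0.50 | 0.25 |
| 19.3% | 1.52 | 1.01 | 0.51 |

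The most DLT subjects possible in Cohorts 1 and 2 is 7: Cohort 1 with 0 of 3, Cohort 2 with 1 of 3 and then 3 of 3, and the Cohort 1 top-up with 3 of 3.

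These figures count subjects with a DLT and a dose still due. They do not count subjects who would be re-dosed, which the documents give no basis to estimate.

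**The case against.** The strongest reply is that the permissive verb is generic list wording. The same lead-in covers withdrawal of consent, loss to follow-up, AEs that by their own description require discontinuation, and pregnancy, for which Section 8.3.1 expressly calls for an immediate stop. None of these is really optional. Sections 3.1 and 5.1.9 point toward stopping, the later-cycle tables show the intent, and no passage supports re-dosing after a DLT. The gravest reactions are already covered in Cycle 1 by the pressor sentence and by Section 5.4.2.

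Most of this stands. A reader might infer that the protocol deliberately permits re-dosing after a DLT; the documents do not support that. What remains is that pregnancy has its express stop elsewhere, while a Cycle 1 DLT has none.

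A reader might also infer that every Grade 3 or greater infusion reaction in Cycle 1 should end treatment. That goes too far. Section 5.1.4 exempts certain Grade 3 fevers and Grade 3 rigors or chills that respond to therapy. A weekly-cohort subject stopped early for an exempt reaction would have neither three doses nor a DLT, would be unevaluable under Section 5.1.6, and would have to be replaced under Section 5.4.1. A mandatory stop for reactions outside the DLT definition could therefore raise enrolment and exposure.

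The prophylaxis text in 5.1.2 item 3 and 4.3.1 is fairly read as managing subjects who continue. It carries no grade limit, however, so it does not close the gap either.

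**Conclusion.** The point holds as a minor patient-safety correction. In the cycle where DLTs are defined, the stated rule is permissive, and the firmer rule begins one cycle later. In Cohorts 1 and 2 this leaves open one or two full doses after a DLT.

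The number of subjects in that position is likely small: roughly 0.1 to 1.0 expected across the assumed rates and timings. The top of that range uses an upper confidence bound as if it were the true rate, whereas the US study observed no DLT. The figures rest on a common DLT rate, full evaluability, no intermediate doses and the assumed timing.

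A reader might suspect an effect on dose escalation or the MTD. There is none: under Section 5.1.6 a subject with a Cycle 1 DLT is evaluable and counts as a DLT whether or not dosing continues.

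**What to change.** - **Section 5.4.1:** state that MEDI-573 will be permanently discontinued for a DLT in Cycle 1; for an AE corresponding to a DLT in later cycles, in line with Tables 3 and 4; and for a Grade 3 or greater allergic or infusion reaction in Cycle 1 that meets the Section 5.1.4 definition of a DLT.
- **Section 5.1.2 item 3 and the matching sentence of Section 4.3.1:** state that prophylaxis before later doses applies only to subjects who are not required to stop under Section 5.4.1.

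The cost is protocol wording in three places. Tying the reaction rule to the DLT definition keeps stopped subjects evaluable, so it creates no replacements. Sample size, visits, the escalation rule and the analyses do not change. The pregnancy item needs no edit because Section 8.3.1 already settles it.

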#### **Subject Evaluation/Follow-up**

A schedule of screening, treatment visit and follow-up visit procedures are presented in [Table 5](#) (Cohorts 1 and 2) and [Table 9](#) (Cohort 3).

The details of the evaluations are shown in Section 6.1.

[figure not shown]
AEs and SAEs during the study will be assessed from the time the subject provides the consent through 30 days after the last dose of MEDI-573. AEs will be graded according to the National Cancer Institute Common Terminology Criteria for Adverse Events Version 4.0 (NCI CTCAE V4.0). In addition, disease evaluations (including computerised tomography (CT) or magnetic resonance imaging (MRI) scans), focused physical examination, and world health organization (WHO) performance status will be performed after every 2 cycles of treatment until documentation of disease progression or initiation of alternative anticancer therapy. For subjects who discontinue treatment due to reasons other than disease progression or initiation

Date

of alternative anticancer therapy, disease evaluations will be performed at 3 months after the last dose of MEDI-573. Subjects will be evaluated for disease response using Response Evaluation Criteria in Solid Tumours (RECIST ver 1.1; [Eisenhauera et al 2009](#)).

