#### **5.4.4 Procedures for withdrawal from study**

A subject that discontinues will always be asked about the reason(s) for discontinuation and the presence of any AEs. The Principal Investigator or Sub-Investigator will perform the best possible observation(s), test(s) and evaluation(s) as well as give appropriate medication and all possible measures for the safety of the subject. They will also immediately inform AstraZeneca of the withdrawal. AEs will be followed up (see Sections 6.4.3 and 6.4.4).

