### **6.3.6 Follow-up**

A post study assessment will be performed at the time investigational product is permanently discontinued (see [Table 5](#) and [Table 9](#)).

In addition subjects should be followed up at 30 days after the last dose of study treatment for any new reports of AEs. Subjects should also be asked about concomitant medications at this follow-up. IM and preliminary anti-tumour activity will be evaluated at the follow-up, which occurs 3 months after the last dose (see [Table 5](#) and [Table 9](#)).

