### **6.4.3 Recording of adverse events**

#### **Time period for collection of AEs**

All AEs will be collected throughout the study, from informed consent until the end of the follow-up period. The follow-up period is defined as 30 days after the end of study treatment.

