### **7.7.1 Objective response and disease control**

ORR is defined as the proportion of subjects with confirmed CR or confirmed PR according to RECIST ver1.1. Confirmed responses are those that persist on repeat imaging study  $\geq 4$  weeks after the initial documentation of response.

TTR will be measured from the start of treatment with MEDI-573 to the first documentation of objective response and will only be assessed in subjects who have achieved objective response.

DR will be defined as the duration from the first documentation of objective response to the first documented disease progression. DR will only be calculated for the subgroup of subjects with an objective response during the study period (until 3 months after the last dose).

TTP will be measured from the start of treatment with MEDI-573 until the documentation of disease progression during the study period (until 3 months after the last dose).

PFS will be measured from the start of treatment with MEDI-573 until the documentation of disease progression or death due to any cause, whichever occurs first during the study period (until 3 months after the last dose).

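### Section 5.4.1 says that subjects who stop MEDI-573 leave the study, which contradicts the 30-day and 3-month assessments required after the last dose

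*Protocol*

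**What the plan says.** Section 5.4.1 lists the reasons for stopping the drug and then states, without exception: "Subjects who are permanently discontinued from investigational product will discontinue the study". It refers to Section 5.4.4, the procedures for withdrawal from the study. Section 5.4.4 asks the site to record the reason for stopping, make the best possible observations and tests, inform the sponsor, and continue AE follow-up: "AEs will be followed up (see Sections 6.4.3 and 6.4.4". It mentions no 30-day or 3-month visit.

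Other parts of the protocol require assessments after the last dose:

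- Section 3.1, for subjects who stop for reasons other than progression or alternative anticancer therapy: "disease evaluations will be performed at 3 months after the last dose of MEDI-573". Footnote e of Tables 5 and 9 says the same.
- Section 6.3.6, after an assessment at permanent discontinuation: "In addition subjects should be followed up at 30 days after the last dose of study treatment for any new reports of AEs", and then "IM and preliminary anti-tumour activity will be evaluated at the follow-up, which occurs 3 months after the last dose".
- Section 6.4.3, on AE collection: "The follow-up period is defined as 30 days after the end of study treatment".
- Section 7.7.1, on PFS: "whichever occurs first during the study period (until 3 months after the last dose". DR and TTP use the same window.
- Tables 5, 9, 13 and 14 schedule a 30-day and a 3-month time point, both counted from the last dose. Table 19 budgets blood for them from each subject.

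**The concern.** Under Section 3.1, dosing continues until toxicity, progression or another reason for withdrawal. Every subject therefore eventually stops the drug permanently, and the sentence in 5.4.1 applies to all of them. The two follow-up visits exist only for subjects in that position. A site that follows 5.4.1 and 5.4.4 as written would not hold visits that Tables 5 and 9 require.

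Immunogenicity, PK and anti-tumour activity are secondary objectives, and the 30-day laboratory, vital-sign and ECG checks contribute to the primary safety objective. This cannot be left to the analysis stage, because a sample that was never drawn cannot be recovered there.

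**Working it through.** **1. Who is affected.** Planned size is 3 cohorts × 3 to 6 = 9 to 18 evaluable subjects (Section 3.1, Table 2). Both visits are timed from the last dose. On the literal wording of 5.4.1, 0 of 9 to 18 subjects are still in the study when they fall due.

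**2. What survives and what does not, on the literal wording.**

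| Item | Source | Survives? |
|---|---|---|
| AEs to 30 days, and follow-up of unresolved AEs | 5.4.4, which points to 6.4.3 | Yes |
| Deaths to 30 days after the last dose | 6.4.3 | Yes |
| End-of-treatment scan, laboratory tests, vital signs, ECG, PK | 6.3.6, Tables 5 and 9 | Yes |
| 30-day laboratory tests, vital signs, ECG, PK, antibodies | Tables 5, 9, 13, 14 | No |
| 3-month antibody sample, all subjects | Tables 5, 9, 13, 14 | No |
| 3-month tumour assessment, only if stopped for reasons other than progression or alternative therapy | 3.1, footnote e | No |

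**3. Antibody samples.** Tables 13 and 14 place them pre-dose on Cycle 1 Day 1, pre-dose on Day 1 of later cycles, at 30 days and at 3 months. None is marked at end of treatment. Footnote d of Tables 5 and 9 asks for all possible measures at that visit, but Table 19 budgets only two antibody samples (2 × 8.5 = 17 mL) across end of treatment, 30 days and 3 months. The 30-day and 3-month draws account for both. A subject who stops in Cycle 1 has one sample, taken before the first infusion (Table 16 also counts one), so the number of post-exposure samples left is 0.

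The protocol's own animal data show that a late response can occur. In the 13-week monkey study (Section 2.2.1), one high-dose animal was antibody-positive on Day 135. Assuming 13 weekly doses starting on Day 1, the last dose fell on Day 1 + 12 × 7 = Day 85, so that result came 135 − 85 = 50 days after dosing. This is one animal and serves only as illustration.

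**4. Blood volume.** Table 19 is reproduced first, in the order chemistry, haematology, PK, antibodies, sponsor biomarkers, soluble protein, tumour markers:

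- Planned: 10 + 5.2 + 8 + 17 + 32 + 10 + 7 = 89.2 mL, as stated.
- End of treatment only: 5 + 2.6 + 4 + 0 + 16 + 5 + 3.5 = 36.1 mL.
- Removed: 89.2 − 36.1 = 53.1 mL, and 53.1 / 89.2 = 59.5%.

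For a subject with no tumour-marker draws (Table 19 makes them depend on the tumour), the figures are 82.2 planned, 32.6 kept and 49.6 removed, or 60.3%.

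**5. Dose decisions.** DLTs are assessed from Cycle 1 Day 1 to Day 21 (Section 5.1.4). The earliest possible last dose is Day 1, and 30 days later is Day 31. AE collection under 6.4.3 therefore covers the whole DLT window even for a subject who stops at once.

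**The case against.** The strongest reply is that the intent is clear. Section 6.3.6 deals with this very situation, and it calls the assessment at permanent discontinuation a post-study assessment. Leaving the study in 5.4.1 could then mean leaving the treatment phase. The provisions in 3.1, in footnote e and in Tables 13, 14 and 19 are specific, and a specific instruction would normally prevail over one general sentence. Many sites would simply follow the schedule.

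That makes actual loss less likely, but it does not remove the conflict. Section 5.4.1 sends the site to the withdrawal procedures, and its next sentences use withdrawal from the study in the ordinary sense when they discuss replacement. Section 5.4.4 does not point to 6.3.6.

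The reply does limit the consequences. A reader might infer that post-treatment AEs would be lost. The documents do not support this, because 5.4.4 keeps AE follow-up through 6.4.3. A reader might also infer that PFS, TTP and DR would be cut at the last dose for everyone. That goes too far: a scan is scheduled at end of treatment, and no 3-month scan was ever required of subjects who stopped for progression or started alternative therapy.

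**Conclusion.** The contradiction stands and should be corrected. It is a conflict of wording in an otherwise complete follow-up schedule. On the literal reading, each subject loses both post-treatment antibody samples, the 30-day laboratory, vital-sign, ECG and PK assessments, and about 60% of the blood volume planned from end of treatment onward.

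The loss for PFS, TTP and DR is confined to subjects who stop without progression and without alternative therapy, which includes stops for toxicity, and to deaths between 30 days and 3 months. The protocol gives no basis for predicting how many such subjects there will be. One subject is 1/18 to 1/9 (5.6% to 11.1%) of the planned number. That is the weight of a single case and not an estimate of the loss.

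A reader might infer that all 30-day and 3-month data would disappear. That would require sites to disregard 6.3.6 and every schedule table, and it would still overlook the AE data that 5.4.4 retains. Nor does the point reach dose escalation: DLT, escalation and MTD decisions rest on Cycle 1 and are unaffected. The figures assume that 5.4.1 is applied literally and that the end-of-treatment assessments are done as scheduled.

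**What to change.** Reword the sentence in 5.4.1 along these lines: *Subjects permanently discontinued from MEDI-573 stop study treatment and enter follow-up. They complete the end-of-treatment, 30-day and 3-month assessments that apply to them under Tables 5 and 9, including footnote e, unless they withdraw consent (including under Section 6.8.5), are lost to follow-up or die.* The reference to 6.8.5 is needed because that section ends participation for a subject who withdraws consent to mandatory samples. Section 5.4.4 should refer to 6.3.6.

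Two related passages must be reconciled in the same edit:

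- Section 4.3.1 bars anticancer drugs for as long as the subject is in the study, while footnote e foresees subjects who start such therapy after stopping MEDI-573. The text must say which period the bar covers.
- Section 5.5 follows subjects still on drug at the data cut-off for new AEs for 3 months after the last dose, whereas 6.4.3 sets 30 days.

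The cost is one reworded sentence, one cross-reference and these two clarifications. No visit, sample or subject is added: Table 19 stays at 89.2 mL and the planned size at 9 to 18.
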